3.5.2.2 Laboratory Evaluation

3.5.2.2.1 CBC with differential

- 3.5.2.2.2 Acute panel
- 3.5.2.2.3 Hepatic panel
- 3.5.2.2.4 Mineral panel
- 3.5.2.2.5 Lipid panel, amylase/lipase, urinalysis (Month 12 only)
- 3.5.2.2.6 Quantitative Immunoglobulins and IgG subclasses (Month 12 only)
- 3.5.2.2.7 Serum pregnancy test in post-menarchal females
- 3.5.2.2.8 CD4 percent and absolute cell count
- 3.5.2.2.9 HIV-1 RNA levels (HIV-infected patients only)
- 3.5.2.3 Research Evaluation
 - 3.5.2.3.1 Serum for HPV antibody titers performed by Merck (Months 7 and 12 only. Competitive luminex assay). 10ml RTT
 - 3.5.2.3.2 Studies to be performed by [name], NCI, Frederick (all subjects)
 - 3.5.2.3.2.1 Functional HPV antibody neutralization assays.
 - 3.5.2.3.2.2 Cryopreserved PBMCs (6 tubes sodium heparin 10ml GTT) for:
 - 3.5.2.3.2.2.1 HPV & HIV lymphocyte proliferation assays
 - 3.5.2.3.2.2.2 Cytokine induction assay
 - 3.5.2.3.2.2.3 Luminex multi-cytokine profiling of PBMCs
 - 3.5.2.3.3 Extended FACS/Quantitative lymphocyte subpopulation studies: 10ml sodium heparin GTT as outlined in 3.5.1.3.4 (HIV-infected subjects only)
 - 3.5.2.3.4 Serum Storage 10ml RTT (Leidos): for [name] functional HPV neutralization antibody assay and for possible later quantitative measurement of HIV-related chemokines MIP-1 α , MIP-1 β and RANTES
 - 3.5.2.3.5 Whole blood for HPV DNA testing Dark Lavender K₂ EDTA, collect 3 tubes (18ml total), Drs. [name] & [name] (Months 7 and 12 only)
- 3.5.3 Follow-Up Study Visits After Year 1: Months 18, 24, 30, 36, 42 and 48 (\pm 30 days).
 - 3.5.3.1 Clinical Evaluation
 - 3.5.3.1.1 Review of systems and documentation of symptoms. β
 - 3.5.3.1.2 Height and weight.
 - 3.5.3.1.3 Vital signs.
 - 3.5.3.1.4 Directed physical examination including skin exam and lymph node survey and documentation of any abnormalities.
 - 3.5.3.1.5 Gynecologic evaluation, cervical cytology (Pap smear) and HPV DNA testing (Months 24, 36 and 48; sexually active females only)
 - 3.5.3.2 Laboratory Evaluation
 - 3.5.3.2.1 CBC with differential

- 3.5.3.2.2 Acute panel
- 3.5.3.2.3 Hepatic panel
- 3.5.3.2.4 Mineral panel
- 3.5.3.2.5 Quantitative Immunoglobulins and IgG subclasses (Months 24, 36 and 48)
- 3.5.3.2.6 Lipid panel, amylase/lipase, urinalysis (Months 24, 36 and 48)
- 3.5.3.2.7 Serum pregnancy test in post-menarchal females
- 3.5.3.2.8 CD4 percent and absolute cell count
- 3.5.3.2.9 HIV-1 RNA levels (HIV-infected patients only)
- 3.5.3.3 Research Evaluation
 - 3.5.3.3.1 Serum for HPV antibody titers performed by Merck (Months 24 and 48 only Competitive luminex assay). 10ml RTT
 - 3.5.3.3.2 Studies to be performed by [name], NCI, Frederick (all subjects; Months 24, 36, 48 only)
 - 3.5.3.3.2.1 Functional HPV antibody neutralization assays.
 - 3.5.3.3.2.2 Cryopreserved PBMCs (6 tubes sodium heparin 10ml GTT) for:
 - 3.5.3.3.2.2.1 HPV & HIV lymphocyte proliferation assays
 - 3.5.3.3.2.2.2 Cytokine induction assay
 - 3.5.3.3.2.2.3 Luminex multi-cytokine profiling of PBMCs
 - 3.5.3.3.3 Extended FACS/Quantitative lymphocyte subpopulation studies: 10ml sodium heparin GTT as outlined in 3.5.1.3.4 (HIV-infected subjects only)
 - 3.5.3.3.4 Serum Storage 10ml RTT (Leidos): for [name] functional HPV neutralization antibody assay and for possible later quantitative measurement of HIV-related chemokines MIP-1 α , MIP-1 β and RANTES
 - 3.5.3.3.5 Whole blood for HPV DNA testing 6ml Dark Lavender K₂ EDTA, collect 3 tubes (18ml total), Drs. [name] & [name] (Months 24, 36 and 48 only)

3.6 CONCURRENT THERAPIES

3.6.1 Contraindicated Therapies

- 3.6.1.1 Pharmacologic doses of immune modulating agents including IVIG. Patients requiring oral corticosteroids for management of severe asthma or contact hypersensitivity for \leq 14 days in duration will be allowed to receive them on study. Patients must not have received oral steroids within 14 days prior to receipt of quadrivalent HPV vaccination. Topical steroids, such as creams and lotions, as well as inhaled steroids, are permitted.
- 3.6.1.2 Cyclophosphamide, hydroxurea, methotrexate or other immunosuppressive drugs.
- 3.6.1.3 Recombinant cytokines or growth factors

3.6.2 Allowed Therapies

Study subjects will be allowed to take multivitamins, oral contraceptives, and other medications as clinically indicated. Use of herbal or nutritional supplements is discouraged. For females taking oral contraceptives that are also receiving HAART, study investigators will verify that their contraceptives do not interfere with any antiretroviral drugs in their current HAART regimen. In clinical studies of GARDASIL®, use of hormonal contraceptives or lack of use of hormonal contraceptives among study participants did not alter vaccine efficacy.⁸³ Results from clinical studies also indicate that GARDASIL® may be administered concomitantly (at a separate injection site) with recombinant hepatitis B vaccine. Although co-administration of GARDASIL® with other vaccines has not been studied, ACIP Recommendations state that the vaccine may be given at the same visit when other age appropriate vaccines are provided such as Tdap, Td and MCV4.⁸⁴ For HIV-infected study subjects, it is anticipated that there will be no need for HIV-related OI prophylaxis given the high CD4 cell count entry criteria to enroll on study.

3.7 OFF TREATMENT AND OFF STUDY CRITERIA

- Off Treatment- Any Grade III or higher toxicity possibly or probably related to vaccine that does not resolve to baseline within 4 weeks with appropriate intervention.
- Off Treatment- Any Grade IV toxicity unrelated to vaccine that does not resolve to within grade 1 or lower within 8 wks.
- Off Treatment- Severe or life-threatening immediate hypersensitivity reactions following receipt of quadrivalent HPV vaccine.
- Off Treatment and Off Study- Development of an acute life-threatening condition or cancer.
- Off Treatment and Off Study- Inability to adhere to HAART.
- Off Treatment and Off Study- Discontinuation of HAART for >6 wks due to antiretroviral toxicity.
- Off Treatment- > 30% decrease in baseline CD4 cell count or percent or decrease in absolute CD4 count to < 350 cells/mm³ confirmed by at least 2 measurements 4 weeks apart.
- Off Treatment- Increase in HIV-1 RNA levels to > 100,000 copies/ml confirmed by at least 2 measurements 4 weeks apart.
- Off Treatment- Pregnancy. Patients will be taken off-study and advised to defer completion of their vaccination regimen until resolution of the pregnancy. Patients will also be reported to the Merck Pregnancy Registry [contact]) that monitors fetal outcomes of pregnant women exposed to GARDASIL®.
- Off Study- Non-compliance with study protocol evaluations and visits.
- Off Study- Study discontinuation at the request of the patient or at the discretion of the Principal Investigator or Lead Associate Investigator if they determine that study withdrawal is in the patient's best interest.

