3.2.2 Quadrivalent HPV (types 6, 11, 16, 18) Recombinant Vaccine Administration

Quadrivalent HPV vaccine will be administered intramuscularly as 3 separate 0.5ml doses, in single use, prefilled syringes at 0, 2 and 6 months (\pm 2 weeks) in an outpatient clinic setting. Vaccine should be administered intramuscularly in the deltoid region of the upper arm or in the higher anterolateral area of the thigh. Thorough agitation immediately before administration is necessary to maintain suspension of the vaccine. Following thorough agitation, the vaccine is a white cloudy liquid. The vaccine should not be administered if particulate matter is present or if it appears discolored. Patients will remain under nursing observation for 2 hours following the first injection. Vaccine-related adverse reactions will be evaluated using vaccination report card (VRC)-aided surveillance for 14 days after each dose of quadrivalent HPV (types 6, 11, 16, 18) recombinant vaccine in all study subjects. Per the ACIP Recommendations for the Use of Quadrivalent HPV Vaccine, the vaccine can be administered at the same visit when other age appropriate vaccines are indicated, such as Tdap, Td and MCV4.⁸⁴ Study subjects with minor acute illnesses e.g. upper respiratory tract infections or diarrhea with a temperature $< 101^{\circ}\text{F}$, will be allowed to receive vaccine. Vaccination will be deferred for individuals with moderate or severe acute illnesses and/or temperature $\geq 101^{\circ}\text{F}$ until after the illness resolves.

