4.2 VACCINE-RELATED EVENTS

Appropriate evaluation of and supportive care for immediate hypersensitivity reactions as well as delayed adverse reactions to quadrivalent HPV vaccination will be made according to standard care.

Study subjects that have objective of immediate hypersensitivity to the quadrivalent HPV vaccine or any of its components will not receive further doses of vaccine.

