7.2 RELATIONSHIP TO THERAPY

The Principal Investigator will assess whether the AE or SAE is associated with the administration of quadrivalent HPV (Types 6, 11, 16, 18) recombinant vaccine:

- “Related” includes, possible, probably, and definitely related events.
- “Not related” includes unlikely and not related.

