7.3.2 NIH Intramural IRB Requirements for PI Reporting at Continuing Review

The protocol PI will report to the NIH Intramural IRB:

1. A summary of all protocol deviations in a tabular format to include the date the deviation occurred, a brief description of the deviation and any corrective action.
2. A summary of any instances of non-compliance
3. A tabular summary of the following adverse events:
 - All Grade 2 **unexpected** events that are possibly, probably or definitely related to the research;
 - All Grade 3 and 4 events that are possibly, probably or definitely related to the research;
 - All Grade 5 events regardless of attribution;
 - All Serious Events regardless of attribution.

NOTE: Grade 1 events are not required to be reported.

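### The Section 3.7 stopping rule for vaccine toxicity names possibly and probably related events but leaves out definitely related ones

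*Combined protocol and SAP*

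**What the plan says.** The first bullet of Section 3.7 (Off Treatment and Off Study Criteria) ends vaccination for "Any Grade III or higher toxicity possibly or probably related to vaccine that does not resolve to baseline within 4 weeks" with appropriate intervention. The second bullet ends it for "Any Grade IV toxicity unrelated to vaccine that does not resolve to within grade 1 or lower within 8 wks".

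The attribution scale is set out elsewhere. Section 7.2 has the Principal Investigator judge each adverse event against the vaccine and says that the related class "includes, possible, probably, and definitely related events". Section 7.3.2, on reporting at continuing review, asks for "All Grade 3 and 4 events that are possibly, probably or definitely related to the research".

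Several other provisions bear on whether a participant with a toxicity receives another dose:

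- Section 3.7 has an Off Treatment bullet for severe or life-threatening immediate hypersensitivity, and two more for a confirmed CD4 decline and a confirmed rise in HIV-1 RNA.
- Section 3.7 also has an Off Treatment and Off Study bullet for "Development of an acute life-threatening condition or cancer".
- Section 3.7 allows Off Study removal "at the discretion of the Principal Investigator or Lead Associate Investigator if they determine that study withdrawal is in" the patient's best interest.
- Section 4.2 says that subjects who "have objective of immediate hypersensitivity to the quadrivalent HPV vaccine or any of its components will not receive further doses of vaccine".
- Section 3.2.2 says "Vaccination will be deferred for individuals with moderate or severe acute illnesses" until the illness resolves.
- Section 2.3 lets the participant decline a dose at any time.

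**The concern.** The first bullet of Section 3.7 does not use the defined term *related*, which would have brought in all three levels. It names two of them. The remaining level, the strongest, falls outside this bullet, and the second bullet cannot catch it because that one is confined to unrelated events.

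The literal result is inverted: dosing must stop on a weaker suspicion of vaccine causation and need not stop on a firm one. Section 3.7 is the operative list for ending vaccination in an individual participant. Section 7.5.1 considers neither a single independent monitor nor a data and safety monitoring board to be warranted, so these individual criteria carry much of the safety load. What is at stake is a further dose given to someone with a persisting severe toxicity already attributed to the vaccine.

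**Working it through.** No sample size, power, alpha or event count enters this point, so the check is a comparison of texts.

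**Step 1: which attribution levels does each provision name?**

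| Level | 3.7, first bullet (Grade III or higher) | 3.7, second bullet (Grade IV) | 7.2, related | 7.3.2, Grade 3 and 4 |
|---|---|---|---|---|
| Possible | yes | no | yes | yes |
| Probable | yes | no | yes | yes |
| Definite | **no** | no | yes | yes |

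The word *definitely* appears nowhere in Section 3.7. One of the three related levels in Section 7.2 is therefore missing from the dosing rule.

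**Step 2: does any other provision force a dosing stop for the missing level?** Take a definitely related Grade III event, unresolved at 4 weeks.

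- *Hypersensitivity (3.7 and 4.2):* only if the event is an immediate hypersensitivity reaction.
- *Life-threatening condition or cancer (3.7):* does not reach a Grade III event that is not life-threatening.
- *CD4 and HIV-1 RNA bullets (3.7):* apply whatever the attribution, but only to those two measures.
- *Deferral (3.2.2):* applies to moderate or severe acute illness or a temperature of 101°F or above. It postpones a dose and does not end the series.
- *Investigator discretion (3.7):* available, but optional. It is labelled Off Study, so it removes the participant from the study and not only from dosing.
- *Right to decline (2.3):* the participant's choice, not a protocol safety rule.

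What is left is a definitely related, persistent Grade III or higher event that is not life-threatening, not hypersensitivity, not an acute illness, and not a CD4 or HIV-1 RNA change. A hepatic laboratory toxicity is the plain example.

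**Step 3: could such an event arise and be seen before another dose?** Yes. Hepatic panels are scheduled at months 1 and 2 (Sections 3.5.1.2 and 3.5.2.2; Appendices 2A and 3A), and Section 7.5.1 has all on-study laboratory data graded by CTCAE and reviewed. Doses are at months 0, 2 and 6. A toxicity that starts soon after dose 1 can pass the 4-week limit before dose 2, and one that starts after dose 2 has about 4 months before dose 3.

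**Step 4: how much dosing is exposed?** The rule can only affect doses given after a toxicity has appeared, so at most 3 − 1 = 2 of the 3 doses (doses 2 and 3).

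**The case against.** The strongest reply is that the wording sets a floor of suspicion. If possible relatedness is enough to stop, definite relatedness is enough a fortiori, and no sensible investigator would stop for a suspected cause and carry on for a confirmed one. Sections 7.2 and 7.3.2 also serve adverse event assessment and review-board tabulation, not dosing, and Section 3.7 cites neither. That is persuasive on intent, and it is why harm is unlikely. It does not correct the rule: the bullet lists named levels from a scale the investigator has to apply, and it has no wording such as *at least*.

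A second reply is that the safeguards are broad. Besides those in Step 2, Section 7.4.4 sends adverse vaccine reactions to outside bodies within 10 working days, and Section 5.1 follows all adverse events to baseline or stabilization. Section 3.8.3 provides extra follow-up after withdrawal for toxicity, so the protocol plainly contemplates such withdrawals. All of this stands and narrows the gap considerably. Reporting and follow-up do not stop a dose, however, and the discretionary route does so only if the investigator chooses it. The objection is right that the Off Study label does not mean dosing would continue. The drawback of that route is that it is optional and also ends study participation.

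A third reply is that the current version is dated January 2019 and records the IND as withdrawn in April 2018, so few or no doses may remain. The documents do not say whether vaccination has finished, so this cannot be settled from them.

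**Conclusion.** The concern holds as a minor drafting error in an operative safety rule. The first bullet of Section 3.7 omits one of the three related categories that the protocol itself defines. Taken literally, that leaves no mandatory Off Treatment stop for a narrow class of definitely related, unresolved Grade III or higher events.

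The size of the risk cannot be estimated, because the documents give no rate for such events. The conclusion rests on the literal wording; the intended meaning is almost certainly *at least possibly related*, and most investigators would apply it that way. No planned analysis or power statement is affected, and the accrual stopping rule in Section 6.7 uses only CD4 count and HIV-1 RNA.

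**What to change.** In the first bullet of Section 3.7, change the attribution phrase to *possibly, probably or definitely related to vaccine (as defined in 7.2)*, and leave the grade, the 4-week limit and the intervention clause as they are. The dosing rule then matches the protocol's own definition and its reporting language.

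The cost is a wording change in one bullet. It needs no new data, visits or procedures.

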3.8 POST TREATMENT EVALUATION / FOLLOW-UP

This study is 4 years in duration. At the final, month 48, study end-point, study participants will be 42 months out from completion of their vaccination series and no further follow-up or post study evaluations will be performed. For those subjects who meet off-study criteria prior to study completion, the following evaluations will be performed within 8 weeks of being taken off-study.

3.8.1 Clinical Evaluation

3.8.1.1 Comprehensive review of systems and directed physical examination with documentation of abnormalities.

3.8.2 Laboratory Evaluation

3.8.2.1 CBC with differential, platelet count

3.8.2.2 PT, PTT

3.8.2.3 Acute panel

3.8.2.4 Hepatic panel

3.8.2.5 Mineral panel

3.8.2.6 Lipid panel

3.8.2.7 Amylase, lipase

3.8.2.8 Urinalysis

3.8.2.9 Quantitative Immunoglobulins and IgG subclasses

3.8.2.10 CD4 percent and absolute cell count

3.8.2.11 HIV-1 RNA levels by RT PCR (for HIV-infected patients)

3.8.3 Optional Research Evaluation

3.8.3.1 Serum for HPV antibody titers performed by Merck (competitive luminex assay).

3.8.3.2 Quantitative lymphocyte subpopulation studies as outlined in 3.5.1.3.4 (HIV-infected study subjects only).

3.8.3.3 Serum for storage (Leidos) for possible later quantitative measurement of HIV-related chemokines MIP-1 α , MIP-1 β and RANTES.

3.8.3.4 Whole blood for HPV DNA testing 6ml PT EDTA, collect 3 tubes (18ml total), Drs. [name] & [name].

Additional follow-up may be conducted at the discretion of the Principal Investigator or Lead Associate Investigator if study withdrawal was due to toxicity and additional monitoring is warranted until satisfactory resolution is achieved.

4 SUPPORTIVE CARE

4.1 ANTIRETROVIRAL THERAPY

Appropriate evaluation and supportive care for toxicity, intolerance, hypersensitivity or other clinical adverse events related to antiretroviral therapy (for those receiving it) will be made according to standard of care.

4.2 VACCINE-RELATED EVENTS

Appropriate evaluation of and supportive care for immediate hypersensitivity reactions as well as delayed adverse reactions to quadrivalent HPV vaccination will be made according to standard care.

Study subjects that have objective of immediate hypersensitivity to the quadrivalent HPV vaccine or any of its components will not receive further doses of vaccine.

4.3 CYTOLOGIC SCREENING AND MANAGEMENT OF ABNORMAL CERVICAL CYTOLOGIC FINDINGS

All sexually active female study subjects will undergo routine gynecologic evaluation, Pap smear testing (includes endocervix, exocervix and vaginal sampling) and HPV DNA testing. Due to the increased prevalence of cytologic abnormalities and SIL in women with HIV, sexually active, HIV-infected female study subjects will undergo comprehensive gynecologic evaluation, Pap smear and HPV DNA testing *annually* for the duration of the study, as recommended per CDC STD and HPV screening guidelines.⁷⁴ Sexually active, healthy, HIV-negative female control subjects will undergo cervical cancer screening according to published guidelines: American Cancer Society,¹⁰⁰ U.S. Preventive Services Task Force¹⁰¹ and the American College of Obstetricians and Gynecologists.¹⁰² Study subjects found to have abnormal cytology (ASCUS, LSIL including CIN1, or HSIL including carcinoma in situ, CIN2 and 3) will be managed according to Clinical Management Guidelines for Management of Abnormal Cytology and Histology⁹⁹ and in consultation with [name], Chief, CC Gynecology Consult Service.

5 DATA COLLECTION AND EVALUATION

5.1 DATA COLLECTION

The PI will be responsible for overseeing entry of data into an in-house password protected electronic system C3D and ensuring data accuracy, consistency and timeliness. The principal investigator, associate investigators/research nurses and/or a contracted data manager will assist with the data management efforts. All data obtained during the conduct of the protocol will be kept in secure network drives or in approved alternative sites that comply with NIH security standards. Primary and final analyzed data will have identifiers so that research data can be attributed to an individual human subject participant.

All adverse events, including clinically significant abnormal findings on laboratory evaluations, regardless of severity, will be followed until return to baseline or stabilization of event. Patients will be followed for adverse events for 30 days after removal from study treatment or until off-study, whichever comes first.

An abnormal laboratory value will be recorded in the database as an AE **only** if the laboratory abnormality is characterized by any of the following:

- Results in discontinuation from the study
- Is associated with clinical signs or symptoms
- Requires treatment or any other therapeutic intervention
- Is associated with death or another serious adverse event, including hospitalization.
- Is judged by the Investigator to be of significant clinical impact
- If any abnormal laboratory result is considered clinically significant, the investigator will provide details about the action taken with respect to the test drug and about the patient's outcome.

End of study procedures: Data will be stored according to HHS, FDA regulations and NIH Intramural Records Retention Schedule as applicable.

Loss or destruction of data: Should we become aware that a major breach in our plan to protect subject confidentiality and trial data has occurred, the IRB will be notified.

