3.3 TREATMENT MODIFICATIONS

3.3.1 Antiretroviral Therapy

Cohort 1 HIV-Infected Patients on HAART

In the event that a *change* in antiretroviral therapy is warranted based on clinical, immunologic (CD4 count) or viral (HIV-1 RNA levels) parameters, regimen changes will be:

- Made after non-adherence to the current treatment regimen has been *ruled out* as a reason for the observed changes in clinical, immunologic or viral parameters warranting the change in therapy.
- Implemented according to principles and recommendations outlined in the DHHS treatment guidelines.⁹⁸
- Managed by the patient's referring physician in consultation with the protocol team.

Patients that require a *change* in their antiretroviral treatment regimen *prior to study month 7* and completion of all three quadrivalent HPV vaccinations will be taken off study and will not count towards the accrual ceiling for Cohort 1. Up to 10 additional patients will be allowed to enroll in Cohort 1 as replacements to reach the intended Cohort 1 N= 35. Patients that require a *change* in their antiretroviral treatment regimen *after study month 7* following completion of all three quadrivalent HPV vaccinations will be allowed to remain on study.

In the event that a *substitution* in antiretroviral therapy is warranted based on antiretroviral drug toxicity, regimen changes will be:

- Implemented according to principles and recommendations outlined in the DHHS treatment guidelines.⁹⁸

Patients that require a *substitution* in their antiretroviral treatment regimen, whether *prior to* or *after* completion of all three quadrivalent HPV vaccinations will be allowed to remain on study.

Cohort 2 HIV-Infected Patients on No Therapy

In the event that *initiation* of antiretroviral therapy is warranted based on clinical, immunologic (CD4 count) or viral (HIV-1 RNA levels) parameters, antiretroviral treatment will be:

- Implemented according to principles and recommendations outlined in the DHHS treatment guidelines.⁹⁸
- Managed by the patient's referring physician in consultation with the protocol team.

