Patients that require *initiation* of antiretroviral treatment *prior to study month 7* and completion of all three quadrivalent HPV vaccinations will be taken off study and will not count towards the accrual ceiling for Cohort 2. Up to 10 additional patients will be allowed to enroll in Cohort 2 as replacements to reach the intended Cohort 2 N= 35. Patients that require *initiation* of antiretroviral treatment *after study month 7* following completion of all three quadrivalent HPV vaccinations will be allowed to remain on study.

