3.5.1.2 Laboratory Evaluation

- 3.5.1.2.1 CBC with differential
- 3.5.1.2.2 Acute panel

- 3.5.1.2.3 Hepatic panel
- 3.5.1.2.4 Mineral panel
- 3.5.1.2.5 Serum pregnancy test in post-menarchal females
- 3.5.1.2.6 CD4 percent and absolute cell count

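### Section 5.1 stops collecting new adverse events at off-study, so a participant removed for an ART change or start soon after a dose gets none of the 30 follow-up days; the effect is probably small

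*Combined protocol and SAP*

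**What the plan says.** Section 5.1 (Data Collection) sets the period for collecting adverse events: "Patients will be followed for adverse events for 30 days after removal from study treatment or until off-study, whichever comes first". The same section keeps events that are already open under follow-up until they resolve or stabilise.

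Section 3.3.1 (Antiretroviral Therapy) defines an off-study route that depends on the course of HIV disease. A Cohort 1 participant whose regimen has to be changed for clinical, CD4 or viral reasons before month 7 "will be taken off study and will not count towards the accrual ceiling for Cohort 1". Cohort 2 participants who have to start ART before month 7 are treated the same way, and "Up to 10 additional patients will be allowed to enroll in Cohort 2 as replacements to reach the intended Cohort 2 N= 35". Substitutions made because of drug toxicity do not trigger removal.

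Section 3.7 adds criteria that only HAART users can meet. One reads "Off Treatment and Off Study- Inability to adhere to HAART"; the other is stopping HAART for more than 6 weeks because of toxicity. By contrast, the CD4 and viral-load limits end treatment only, for example "Off Treatment- Increase in HIV-1 RNA levels to > 100,000 copies/ml confirmed by at least 2 measurements 4 weeks apart".

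Two other provisions matter. Section 3.2.2 says: "Vaccine-related adverse reactions will be evaluated using vaccination report card (VRC)-aided surveillance for 14 days after each dose". Section 3.8 says that for anyone who meets off-study criteria early, "the following evaluations will be performed within 8 weeks of being taken off-study". It lists a review of systems, a directed examination and laboratory tests including CD4 and HIV-1 RNA.

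**The concern.** The rule runs the wrong way. A participant who crosses the viral-load limit is off treatment, remains on study and keeps 30 days of collection. A participant whose HIV findings lead the treating physician to change or start ART goes straight off study and keeps none, however recent the last dose. Nothing in the protocol explains the difference.

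The ART-based triggers have no counterpart in Cohort 3. Safety in HIV-infected participants is a primary objective (Section 1.1 and the Precis), and Section 3.1 says the controls allow safety endpoints to be compared. What is at stake is the completeness of the adverse-event record for vaccinated HIV-infected participants whose disease course prompted their removal. Section 6 defines no safety analysis set, so it is also open whether replaced participants stay in the safety tables.

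**Working it through.** **1. The window under Section 5.1.** Days of collection = min(30, days from off-treatment to off-study).
- Off treatment only, still on study at day 30: min(30, 30) = 30 days.
- Removed under 3.3.1, which gives no separate off-treatment date, so the two dates are taken to coincide: min(30, 0) = 0 days.

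**2. Post-dose days lost.** Taking 30 days after the last dose as the yardstick, removal *d* days after that dose loses 30 − *d* days.

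| Removal, days after last dose | Days lost of 30 | Of these, after the 14-day report card ends |
|---|---|---|
| 7 | 23 (77%) | 30 − 14 = 16 |
| 14 | 16 (53%) | 16 |
| 21 | 9 (30%) | 9 |
| 30 or more | 0 | 0 |

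The last column assumes the card is still completed and returned after removal. The plan does not say it stops.

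**3. Can removal fall inside the window?** Yes. The dose visits include "3.5.1.2.6 CD4 percent and absolute cell count", and Appendix 2A also schedules HIV-1 RNA at months 2 and 6. Results from a dose visit can therefore prompt an ART decision within days or weeks of that dose. CD4 and RNA are drawn again at months 1 and 3. With 30.4 days per month, an on-time visit falls 30.4 days after the preceding dose and nothing is lost. A visit 14 days early, as its window allows, falls at 30.4 − 14 = 16.4 days, and removal that day would lose 30 − 16.4 = 13.6 days.

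**4. Illustration of how often.** The documents give no removal times. Suppose, purely as an assumption, that removals are uniform over months 0 to 7 (7 × 30.4375 = 213.1 days), with doses at months 0, 2 and 6.
- Within 30 days of the last dose: 3 × 30 / 213.1 = 42%.
- Within the 14-day card period: 3 × 14 / 213.1 = 20%.
- Mean loss among those within 30 days: 15 days.
- Already past 30 days, so losing none: 100% − 42% = 58%.

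Clustering at on-time month 1 and 3 visits would bring the affected share towards zero; clustering just after dose visits would raise it.

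**5. How many could be removed?** Replacing 1 to 10 participants in an HIV-infected cohort means 1/36 (3%) to 10/45 (22%) of that cohort's enrollees were removed. This is what the replacement allowance permits, not a forecast. The accrual halt in Section 6.7 does not bound it, because that rule counts removals for the CD4 and RNA limits, and an ART decision under 3.3.1 need not meet those limits.

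**6. Does Section 3.8 close the gap?** Only in part. It requires one evaluation up to 8 × 7 = 56 days after off-study. Section 5.1 has by then closed the adverse-event period, and no sentence says that new findings are entered as adverse events.

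**The case against.** The strongest reply is that these participants are still observed. The 3.8 evaluation covers symptoms, examination and laboratory tests, and asks for abnormalities to be documented. The definition in 7.1.1 is broad enough to include what it would find. Extra follow-up is allowed when withdrawal was for toxicity. The report card covers the 14 days in which reactions to a dose are most actively sought, and open events are followed to an end. So a reader who inferred from the 0-day window that removed participants drop out of all safety observation would be going beyond the documents. That part of the reply stands. It does not answer the narrower point, because documenting a finding at 3.8 is not the same as recording it as an adverse event after 5.1 has ended collection.

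A reader might also infer that serious events would be missed. The reporting rules in 7.3.1, 7.4.1 and 7.4.4 state no off-study cutoff, so this is not established.

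Third, the asymmetry between cohorts is partial. Pregnancy, non-compliance, withdrawal, and life-threatening illness or cancer end collection in Cohort 3 as well. A Cohort 1 regimen change also requires non-adherence to be ruled out first, which takes time and pushes some removals past day 30. Both points stand and reduce the size of the problem.

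**Conclusion.** The point holds as a minor improvement to safety reporting. Section 5.1 gives no further adverse-event days to a participant taken off study under 3.3.1 or the HAART criteria in 3.7, and 3.8 does not expressly repair this. The effect is limited to unsolicited or later events in participants removed within 30 days of a dose. Its size cannot be computed, because the documents give neither removal counts nor event rates; given the report card and the 3.8 evaluation, it is probably small. The 0-day result assumes that off-treatment and off-study coincide under 3.3.1, as the text implies.

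Two stronger readings are tempting and not supported. One is that adverse-event rates in the HIV-infected cohorts are understated by some number of percentage points, or that the comparison with controls is biased. Any such figure would rest on invented removal and event rates, and Section 6 plans no between-cohort test of adverse events. The other is that collection ought to run to month 7 for everyone. Month 7 is the cut-off for ART-based removal and an immunogenicity time point; no section makes it an adverse-event window.

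**What to change.** In Section 5.1, replace the clause that ends collection at off-study. Suggested wording: in anyone taken off study, in any cohort, new adverse events are collected through 30 days after the last vaccine dose or the off-study evaluation in Section 3.8, whichever is later, unless consent is withdrawn. Add that new findings at the 3.8 evaluation are recorded as adverse events. State in Section 6 that safety is summarised in everyone given at least one dose, including replaced participants, with events after an ART change shown on a separate line.

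The cost is a few sentences and one contact per removed participant, often met by the 3.8 visit that is already required. The main drawback is interpretive: events after an ART change may reflect the new drugs or HIV progression, which controls cannot have. That is the reason for the separate line.

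The version is dated January 2019 and the IND has been withdrawn (title page and Section 7.5.2), so follow-up may already be complete. In that case, use the all-vaccinated safety set, enter the 3.8 findings that already exist, and report for each cohort the number removed and the days from last dose to off-study.
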